#### 9 ASSESSMENT OF SAFETY

# 9.1 Specification of Safety Parameters

All adverse events reported will be assessed by the PI for the study site in which the participant was enrolled for the severity, expectedness and relatedness, using the criteria listed below.

#### 9.1.1 Adverse Events

- 1. Participant report of loss of confidentiality through the app or its functions
- 2. Participant report of loss of confidentiality through delivery of prevention supplies or commodities
- 3. Participant report of access by others to protected health information through the app or study procedures.
- 4. Participant report of disclosure of status as a research participant due to study-related reminders (from app, phone calls, emails, or text messages).
- 5. Participant report of discomfort or injury due to use of provided specimen collection materials (e.g., finger stick for syphilis testing, self-administered rectal swab or pharyngeal swab).
- 6. Disclosure of personal information about health, sexuality or sexual practices that results in physical violence or threat of violence.
- 7. Disclosure of personal information about health, sexuality or sexual practices that results in adverse effects on employment

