#### 9.1.2 Serious Adverse Events

- 1. Suicidal behavior or intention, including but not limited to following learning the results of study-provided tests (e.g., HIV tests, STI tests)
- 2. Any event that results in death, is life-threatening, results in persistent or significant disability/incapacity, or requires hospitalization or prolongation of existing hospitalization

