# 9.1.4 Severity of Event

Severity will be classified using the following standards:

- Mild: Awareness of the issue, but easily tolerated and are of minor irritant type
  causing no loss of time from normal activities. Incident did not require counseling or
  a medical evaluation; concern on the part of the participant or physical symptoms
  were transient.
- Moderate: Events introduce a low level of inconvenience or concern to the
  participant and may interfere with daily activities, but are usually improved within a
  few days (social harms) or by simple therapeutic measures (injury due to specimen
  collection); moderate experiences may cause some interference with usual activities
  for a few days.
- **Severe:** Events interrupt the participant's normal daily activities and require mental health assessment and treatment (social harms) or clinical treatment (injury due to specimen collection); they usually produce major disruptions in daily activities such as work, school, or family commitments.

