#### 15 ETHICS/PROTECTION OF HUMAN SUBJECTS

#### 15.1 Potential Risks and Benefits

#### 15.1.1 Potential Risks

The potential risks to participants are minimal.

Surveys: Some participants may be uncomfortable answering personal questions, or feel uncomfortable with the HIV prevention topics. Men will have the option for all questions to not answer.

Disclosure of participation in a research study: There is a possibility that someone participating in an online data collection could be identified as participating in research, but this is uncommon. There is some risk that those who participate in online surveys could be observed if they complete the surveys in public, or that data could be at risk during transmission. We will mitigate this risk by reminding participants at the beginning of each survey to complete the survey in a private place, where their responses cannot be observed by others. We will also encourage participants to delete any emails or text messages received as part of the study to protect them from an unauthorized individual viewing the messages.

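### The adverse-event list in Section 9.1.1 has no item for non-serious emotional distress after survey or interview questions or a study-provided test result

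*Combined protocol and SAP*

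**What the plan says.** Section 9.1.1 lists seven adverse events. It gives no general definition, has no 'other' item, and does not say whether the list is complete. The items range from "Participant report of loss of confidentiality through the app or its functions" to "Disclosure of personal information about health, sexuality or sexual practices that results in adverse effects on employment". The only one that mentions discomfort is "Participant report of discomfort or injury due to use of provided specimen collection materials", and its examples are a finger stick and swabs.

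Section 9.1.2 lists two serious adverse events. The first is "Suicidal behavior or intention, including but not limited to following learning the results of study-provided tests". The second is "Any event that results in death, is life-threatening, results in persistent or significant disability/incapacity, or requires hospitalization or prolongation of existing hospitalization".

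Section 15.1.1 describes the risks as minimal and names two. The first concerns the surveys: "Some participants may be uncomfortable answering personal questions, or feel uncomfortable with the HIV prevention topics". The same paragraph lets men skip any question. The second is disclosure of participation.

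Section 9.1.4 makes the absence of any need for counseling part of the mild grade. It reserves the severe grade for events that, among other things, "require mental health assessment and treatment (social harms").

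**The concern.** Three parts of the protocol anticipate psychological reactions: the risk section, the first serious-event item and the severity scale. The list that decides what is logged as an adverse event does not include them unless they are serious or attached to another harm.

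The safety data depend heavily on that list. Section 10 says no DSMB is planned and leaves monitoring to the Principal Investigator and the IRB. Section 11 has the Principal Investigator make sure that adverse event reports are reviewed. A reaction that staff do not recognise as reportable may never become such a report.

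The study also creates the relevant situations. Under Section 8.2, the intervention arm is offered home HIV and STI kits, and study staff give positive STI results by phone. Under Section 7.6, men who seroconvert are interviewed about why they did not start PrEP or why they stopped. Surveys go to both arms. If distress in these settings is not coded, a safety summary with no such events says nothing about whether they occurred, and the description of risk as minimal cannot be checked on this point. Sites may also differ in what they choose to record.

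**Working it through.** The plan states no figure on this point, so the check is a reading of the sections side by side.

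**Step 1. Sort the seven items of Section 9.1.1 by the harm they describe.**

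| Item | Harm | Covers distress from questions or results? |
|---|---|---|
| 1 | Confidentiality lost through the app | No |
| 2 | Confidentiality lost through delivery of supplies | No |
| 3 | Others gaining access to health information | No |
| 4 | Research participation revealed by reminders | No |
| 5 | Discomfort or injury from collection materials | No; the source is the kit, and the examples are physical |
| 6 | Disclosure leading to violence or its threat | No |
| 7 | Disclosure leading to employment harm | No |

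Count: 4 on confidentiality or disclosure of participation + 1 on specimen collection + 2 on consequences of disclosure = 7. Items naming emotional distress: 0 of 7.

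**Step 2. Match the two risks in Section 15.1.1 to the list.** Disclosure of participation has a direct counterpart in item 4 and related ones in items 1 to 3. Discomfort with survey content has none.

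**Step 3. List the ways distress can still reach the safety record.**

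- It is suicidal: first item of Section 9.1.2.
- It is serious in another way, such as a hospital admission: second item of Section 9.1.2, which applies whatever the cause.
- It accompanies a listed social harm, such as a confidentiality loss: it enters with that item and is graded under Section 9.1.4.

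**Step 4. Test the list on illustrative cases.**

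- A man is badly upset after a staff call about a positive STI result and seeks counseling. He is not suicidal or admitted, and nothing has been disclosed. No item applies.
- A man in either arm reports lasting upset after survey questions on sexual behavior. No item applies.
- A man is distressed after an interview about his seroconversion. No item applies.
- A man is admitted to hospital in acute distress without suicidality. The second serious item applies.
- A man is distressed because a reminder revealed that he is in a study. Item 4 applies.

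The first case would be above mild on the scale in Section 9.1.4, because counseling was needed, yet it has no item through which to be graded.

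**Step 5. Check that an added item would fit the relatedness scale.** The opening sentence of Section 9.1.3 covers both the intervention and participation. Its three categories are then worded around exposure to, or use of, the app. Survey distress in a control participant, who under Section 4 has no access to the active app, does not fit them. An added item therefore needs a matching sentence in Section 9.1.3.

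**The case against.** The strongest reply is that the list need not be closed. Section 9.1 says that all reported adverse events are assessed, including for expectedness, and Section 11 has the IRB alerted to unexpected concerns. An investigator could record distress under those provisions, so it cannot be said that distress would never be reviewed. This stands in part. Against it, both items of Section 9.1.2 are worded openly, while Section 9.1.1 has neither open wording nor a catch-all. At best, staff are left to judge whether distress counts.

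Second, Section 15.1.1 speaks of being uncomfortable, not of distress, lets men skip questions, and does not name reactions to test results. Not logging passing discomfort with a skippable question is a defensible choice in a survey and app study. This stands as a limit: the risk section supports the survey part of the point, and the link to test results rests on the first serious item alone.

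Third, serious harm is already captured, and Section 15.8 requires training in delivering STI results. Both are correct. Withdrawal reasons are also recorded (Sections 5.4 and 7.4), though not as adverse events.

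A reader might infer that distress enters the record only once it is suicidal, or that neither serious item can capture non-suicidal distress. The documents do not support this. The second serious item covers any event meeting its criteria, and distress attached to a listed social harm enters with that harm.

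**Conclusion.** The point holds for non-serious distress. None of the seven adverse-event items covers emotional distress after survey or interview questions or after a study-provided HIV or STI result. Such distress is captured only if it is suicidal, otherwise serious, or tied to a listed social harm. This is an inconsistency between Section 9.1.1 and Sections 9.1.2, 9.1.4 and 15.1.1.

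The conclusion assumes that staff record by the list as written. If they treat it as illustrative, the gap becomes one of uneven recording across sites.

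No event count is offered. The documents give no rate of distress, kit uptake or test positivity, so any number would only restate an assumption. The primary outcome, its analysis and the sample size are not affected. The change is worth making because it is cheap and concerns a harm the protocol partly foresees, in a trial without a DSMB.

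**What to change.** Add an eighth item to Section 9.1.1: *Participant report of emotional distress following survey or interview questions, or following receipt of a study-provided HIV or STI test result, not meeting 9.1.2.* Grade it under Section 9.1.4. The word 'following' is deliberate: wording that makes causation part of the definition would prejudge the relatedness that Section 9.1.3 is there to assess.

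In Section 9.1.3, state that relatedness of this item is judged against study participation, which the opening sentence already covers, and not only against exposure to the app. The item then applies in both arms.

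The cost is one line in Section 9.1.1, one sentence in Section 9.1.3, one code on the electronic adverse-event form (Section 16.3) and the IRB review that Section 15.3 requires for any amendment. The downside is a few more mild events to log. No endpoint, schedule or analysis changes.

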#### 9.1.2 Serious Adverse Events

- 1. Suicidal behavior or intention, including but not limited to following learning the results of study-provided tests (e.g., HIV tests, STI tests)
- 2. Any event that results in death, is life-threatening, results in persistent or significant disability/incapacity, or requires hospitalization or prolongation of existing hospitalization

#### 9.1.3 Relationship to Study Intervention

The potential event relationship to the study intervention and/or participation is assessed by the site investigator. A comprehensive scale in common use to categorize an event is:

- Definitely Related: The adverse event is clearly related to the investigational intervention i.e. an event that follows a reasonable temporal sequence from first exposure to the app, follows as a known or expected consequence from using the intervention, and that could not be reasonably explained by the known characteristics of the subject's normal activities.
- Possibly Related: An adverse event that follows a reasonable temporal sequence from exposure to the app, follows a known or expected consequence from use of the app, but that also could readily have been produced by a number of other factors.

Not Related: The adverse event is clearly not related to use of the app - i.e. another
cause of the event is most plausible; and/or a plausible temporal sequence is
inconsistent with the onset of the event and the study intervention and/or a causal
relationship is considered implausible.

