# 5.2.3 Participant Compensation

Compensation for survey completion will be graduated (\$50 baseline, \$40 months 3 and 6, \$50 month 9, \$60 month 12). Study incentives for the baseline will be sent 48-72 hours after completion of the baseline survey to allow for review of data and identification of possible fraudulent or duplicate enrollments. Incentives for IDIs and quarterly follow-up surveys will be processed electronically at the time of interview or survey completion (see Fraud Deterrence). Men in both arms will be asked monthly if they have initiated PrEP; men who report initiating PrEP in either arm will be mailed a dried blood spot collection kit with instructions and a prepaid return mailing envelope, and will be directed to collect and mail a dried blood spot specimen for tenofovir diphosphate detection. Those who return a DBS specimen will be provided with an additional compensation of \$40. Participants will also be asked to take a picture of their prescription or PrEP label; those who provide a photograph will be provided with an additional compensation of \$15. A maximum compensation of \$295 could be provided for completing all of the study visits (\$240), DBS specimen (\$40), and PrEP prescription photo verification (\$15).

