#### 11 CLINICAL SITE MONITORING

The principal investigator will monitor data collection throughout the study, and will ensure that interview protocols are followed, all adverse event reports are reviewed (if any), confidentiality procedures are implemented, and the Emory University IRB is alerted if unexpected concerns arise.

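### The relatedness grades in section 9.1.3 are narrower than their own lead sentence and build expectedness into relatedness, so a few kinds of study-caused event have no correct grade (minor)

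*Combined protocol and SAP*

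**What the plan says.** Section 9.1 has the site's principal investigator assess every reported adverse event "for the severity, expectedness and relatedness, using the criteria listed below". Expectedness and relatedness are thus named as two judgements. Sections 9.1.1 to 9.1.4 then give lists of events, a relatedness scale and a severity scale, but no criteria for expectedness.

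Section 9.1.3 opens broadly: "The potential event relationship to the study intervention and/or participation is assessed by the site investigator". The three grades that follow are narrower:

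- Definitely Related applies where the event "follows a reasonable temporal sequence from first exposure to the app, follows as a known or expected consequence from using the intervention", provided the participant's normal activities could not reasonably explain it.
- Possibly Related needs an event that follows exposure to the app in time and "follows a known or expected consequence from use of the app, but that also could readily have been produced" by other factors.
- Not Related opens with "The adverse event is clearly not related to use of the app". It applies when another cause is most plausible, the timing does not fit, and/or causation is implausible.

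The adverse event list in 9.1.1 includes routes other than the app: supply delivery, study procedures, phone calls, emails and texts. It also includes "Participant report of discomfort or injury due to use of provided specimen collection materials". Section 5.2.3 says that "men who report initiating PrEP in either arm will be mailed a dried blood spot collection kit".

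**The concern.** There are two faults in the wording. First, expectedness is a necessary condition of both related grades, although 9.1 treats it as a separate judgement. The combination of unexpected and related therefore cannot be recorded. Second, the grades leave out the participation half of the lead sentence. A harm caused by the study, but not through the app, is drawn towards Not Related because the study procedure counts as a cause other than the app.

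What is at stake is the accuracy of safety classification. Section 10 plans no data and safety monitoring board, so oversight rests with the principal investigator and the IRB. For non-serious events, section 11 has the investigator review reports and ensure that "the Emory University IRB is alerted if unexpected concerns arise". A scale that cannot mark an event as both unexpected and related gives that review a poorer record to work from.

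**Working it through.** No formula underlies the scale, so the check is to run types of event through the wording of the grades.

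**Conditions.** In Definitely Related and Possibly Related the conditions are cumulative: (a) timing after exposure to the app; (b) a known or expected consequence of using the intervention or app; (c) a statement about other explanations. If (a) or (b) fails, neither grade applies. Not Related requires that the event clearly has nothing to do with use of the app.

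**Cases, read literally.**

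| Event | (a) app exposure | (b) known or expected | Grade that fits |
|---|---|---|---|
| Unexpected event truly caused by the app | yes | no | none: both related grades fail on (b), and it is not clearly unrelated to the app |
| Injury from the dried blood spot kit, either arm | the cause is not the app | not a consequence of using the app | Not Related, because another cause is most plausible |
| Disclosure through a staff call, email or text | the cause is not the app | not a consequence of using the app | Not Related, for the same reason |
| Injury from an STI kit, or disclosure from a supply parcel, intervention arm | yes: ordered through the app (6.1, 8.2.1) | yes: listed in 9.1.1 | a related grade |
| Disclosure through the app shell or its notifications, control arm | yes: shell and same notification format in both arms (6.1.1) | yes: listed in 9.1.1 | a related grade |

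The first three rows go wrong; the last two do not.

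**Number of men exposed to the dried blood spot kit.** It goes only to men who report starting PrEP. Section 12.2 assumes at most 2% uptake in control and 9% in intervention over a year, with 219 and 438 men. The total of 680 at 2:1 gives 680/3 = 226.7 and 453.3.

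- Control: 0.02 × 219 = 4.4; 0.02 × 226.7 = 4.5.
- Intervention: 0.09 × 438 = 39.4; 0.09 × 453.3 = 40.8.
- Both arms: 4.4 + 39.4 = 43.8; 4.5 + 40.8 = 45.3.

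So about 44 to 45 men would be mailed a kit, of whom 4 to 5 are controls, before any allowance for attrition. These are men exposed, not men harmed. The documents give no harm rate for the kit and no count of staff contacts, so the number of misgraded events cannot be calculated.

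**The case against.** The strongest reply is that little depends on the grade. All serious events go to the IRB and the NIDA project officer within 24 hours whatever their relatedness (9.2.1). Confidentiality breaches go to the principal investigator and the IRB at once (16.2). Section 11 has all adverse event reports reviewed, with no relatedness condition. The seven events in 9.1.1 are listed in advance, so most non-serious harms are arguably known already. The lead sentence of 9.1.3 and the mention of specimen-collection injury in 9.1.4 give an investigator textual support for grading procedure harms as related. All of this stands, and it limits the effect.

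It does not remove the defect. The lead sentence may rescue procedure harms if an investigator puts it above the grade definitions, but investigators may differ on that. It does nothing for the known-or-expected condition. A serious event that was unexpected and caused by the app would be reported on time, but with no fitting relatedness grade.

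Three stronger readings are tempting, and the documents do not support them:

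- A reader might infer that no control-arm event can be graded related. Section 4 denies controls the active app, but all men download it, see the same shell, take surveys in it and get the same format of notification (6.1.1, 7.2, 7.3).
- A reader might infer that nearly all the listed adverse events escape the scale. Supplies and STI kits are ordered through the app (6.1, 8.2.1), STI kits are offered to the intervention arm only (8.2), and several listed items name the app as a route.
- A reader might infer that a comparison of related events by arm would be distorted. Section 12 plans no such table, and no analysis or stopping rule uses the grade.

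**Conclusion.** The wording is wrong as it stands, but the consequence is minor. Two groups are affected: unexpected events caused by the app, which have no grade, and harms from the dried blood spot kit or staff contacts, which fall to Not Related in either arm. The result is misclassified or unclassifiable relatedness, mainly for non-serious events. Expedited reporting and the efficacy analysis are unaffected.

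This rests on applying the grade definitions literally. The kit counts also rest on the plan's own uptake assumptions; higher reported uptake would raise them in proportion.

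**What to change.** In 9.1.3:

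- Define all three grades by 'the app, any study procedure or study participation', in either arm, to match the lead sentence. A study procedure then no longer counts as another cause under Not Related.
- In both related grades, replace the known-or-expected condition with 'a causal link is plausible'. Keep the timing condition, reworded to follow exposure to the app or procedure, and keep the conditions on other explanations.
- Record expectedness as its own item, as 9.1 already requires, against a stated reference such as the list in 9.1.1 and the risks in 15.1.1.

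The cost is a wording edit and one field on the reportable-event case report form. The count of related events may rise slightly.

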# 9.1.4 Severity of Event

Severity will be classified using the following standards:

- Mild: Awareness of the issue, but easily tolerated and are of minor irritant type
  causing no loss of time from normal activities. Incident did not require counseling or
  a medical evaluation; concern on the part of the participant or physical symptoms
  were transient.
- Moderate: Events introduce a low level of inconvenience or concern to the
  participant and may interfere with daily activities, but are usually improved within a
  few days (social harms) or by simple therapeutic measures (injury due to specimen
  collection); moderate experiences may cause some interference with usual activities
  for a few days.
- **Severe:** Events interrupt the participant's normal daily activities and require mental health assessment and treatment (social harms) or clinical treatment (injury due to specimen collection); they usually produce major disruptions in daily activities such as work, school, or family commitments.

